10.0 STUDY WITHDRAWAL/DISCONTINUATION

Subjects will be withdrawn from the study for safety considerations, non-compliance with study procedures, difficulties with scheduling or participation, excess movement or anxiety during scanning, or other reasons that the PI or study coordinators conclude will impair the scientific utility of the study. Subjects will be provided an explanation by the investigator if they are withdrawn from the study. In addition, subjects can voluntarily withdraw from the study at any time.

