2.0 RATIONALE AND SPECIFIC AIMS

Our central hypothesis is that in psychotic disorders, LEV will safely normalize hippocampal hyperactivity. This will result in an increase in recruitment and activity of the hippocampus during tasks that specifically engage the hippocampus. In this project, we will test our hypothesis in 40 psychotic patients and 40 healthy control subjects. Following baseline clinical assessments, participants will undergo a 2-way crossover, double-blind, randomized controlled study with low-dose LEV and placebo. We will use neuroimaging methods to test the effect of the intervention.

Study Aim: To determine whether administration of low-dose, oral LEV modulates hippocampal hyperactivity

Hypothesis 1: Oral LEV will decrease, in a dose-response relationship, hippocampal activity in healthy control subjects and psychotic patients (ASL study).

Hypothesis 2: Oral LEV will normalize hippocampal recruitment in patients (Scene-processing fMRI study).

Hypothesis 3: Compared with healthy control subjects, psychotic patients will show higher hippocampal activity (ASL study) and reduced hippocampal recruitment (Scene-processing fMRI study).

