5.2 Monetary Compensation: All study subjects will be remunerated \$25 for completion of the screening and consent form, regardless of their decision to enroll in the study or their eligibility to enroll. Because of the study design, subjects only yield meaningful primary outcome data if they complete all visits. They will therefore be compensated an additional \$275 at the completion of the remaining study visits. This incentivization is designed to yield greater benefit from the research, thereby improving the risk/benefit ratio of the study.

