6.3.d Young Mania Rating Scale (YMRS): an 11-item clinician-rated measure of manic symptoms. Items are rated on various scales using pre-defined anchors ranging from absent to severe. The measure has adequate psychometrics and takes about 20 minutes to complete (Young et al., 1978).

6.4 MRI Procedures: MRI scans of the brain will be obtained using the MRI scanners in the Center for Human Studies in the Vanderbilt University Institute for Imaging Science (VUIIS), located in the Vanderbilt Hospital and Medical Center North. This will require approximately 60-90 minutes. There will be a total of two MRI scans in this study (Visits 2, and 3). During Visits 2 and 3, the participant will be scanned two hours after receiving the study intervention (LEV or placebo).

6.4.a MRI Screening: The participant will fill out the MRI Procedure Screening Form. The purpose of this form is to ensure that there are no implanted medical devices or metals that could injure the subject if exposed to a high magnetic field. This form will be filled out in a private room adjacent to the MRI scanner and reviewed by the MR Technologist and the research assistant.

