6.4.b Scanning Procedures: Imaging studies will take place on a Phillips 3.0 T MRI scanner. The magnet and the magnet's control console are in separate rooms, but the investigator and the subject will be in voice communication at all times, and the investigator will be able to see the subject through a window. All data acquired on the scanner will be securely transferred over the Vanderbilt network to the Institute of Imaging Science's server. Imaging data will be de-identified and only be accessible to the PI, co-investigators, and VUIIS personnel. Scanning procedures may include: 1) Structural imaging, 2) Resting state functional imaging, 3) ASL imaging to non-invasively measure cerebral blood flow, and 4) Functional imaging with task – while in the scanner, participants will view images that include faces, objects and scenes. Images are projected to a mirror above the participants head from a projector located outside the scanner room. Some runs will repeat the same face or object, some runs will present different images. Participants will complete between 1-8 runs of this task. To maximize participant's attention to the images, participants will be instructed to push a button to detect targets. Targets may include image repeats or changes in the image (e.g., image size). This task is similar to the one reported in McHugo et al., 2019.

6.5 Study Drug Administration: During Visit 2, participants will be randomly assigned to an intervention arm in which they will receive two 250mg LEV capsules or two placebo capsules. Both the participant and the research team will be blinded to which arm each participant is in. During Visit 3, the participant will undergo cross-over and receive either two 250mg LEV capsules or two placebo capsules (whichever intervention they did not receive in Visit 2).

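### Does withdrawing people for unquantified movement, with no scan-quality limit or analysis set stated, undermine the LEV-placebo comparison?

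*Combined protocol and SAP*

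**What the plan says.** Section 10.0 lists grounds for withdrawing a person from the study. They include "excess movement or anxiety during scanning, or other reasons that the PI or study coordinators conclude will impair the scientific utility of the study". No measure or threshold of movement is attached, and neither Visit 2 nor partly affected scans are mentioned.

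Section 6.4 schedules two scans, at Visits 2 and 3, and at each "the participant will be scanned two hours after receiving the study intervention (LEV or placebo)". Section 6.5 gives the other condition only later: "During Visit 3, the participant will undergo cross-over". The same section says "Both the participant and the research team will be blinded to which arm each participant is in".

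Section 6.4.b lists ASL and the scene task as separate acquisitions. For the task, "Participants will complete between 1-8 runs of this task". In section 2.0, ASL serves Hypotheses 1 and 3 and the task serves Hypotheses 2 and 3.

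Section 11.2.c specifies realignment, pairwise subtractions and a mixed effects model with group-by-condition interactions. It states no motion limit and no analysis set. The nearest text is in section 5.2, where the payment scheme is justified on the ground that "subjects only yield meaningful primary outcome data if they complete all visits".

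Section 5.1 allows up to 40 people per group and hopes for analysable data from at least 20 in each. Section 11.3 bases its 80.3% power on 20 per group.

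**The concern.** The withdrawal ground removes a person, whereas a movement problem usually affects a run or a series. Both scans follow a randomised capsule, and a person withdrawn at Visit 2 never receives the second condition. If staff withdrew someone because a few task runs were spoiled, a usable ASL pair would be lost too, although ASL answers a different hypothesis.

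The loss occurs after dosing and rests on judgement, so it could in principle depend on the drug. Section 7.1 lists agitation and anxiety among the effects of LEV, though at 1000-3000 mg/day rather than a single 500 mg dose.

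Section 11.2.c also leaves open whether the drug effect is estimated from complete pairs or from all usable scans. Pairwise subtractions suggest the first, if they are LEV minus placebo; a mixed model would permit the second. Two analysts could include different people. At stake would be lost precision, possible selection, and uncertainty about who counts towards the 20 analysable per group.

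**Working it through.** **Inputs from the documents.** Two scans per person (6.4); up to 40 recruited and at least 20 analysable per group (5.1); 80.3% power at 20 per group, alpha 0.05 (11.3). No rate of movement or scan loss is given, so every loss rate below is an assumption.

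**The plan's own figure.** The 80.3% cannot be reproduced, because 11.3 gives no effect size, SD or test. Solving backwards for a two-sided two-sample t test with 20 per group gives a standardised effect of 0.913. With that effect held fixed, 18 analysable per group gives 75.8% power and 16 gives 70.5%. A shortfall below 20 would therefore matter, and the question is whether one is likely.

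**Reaching 20 analysable.** The average number dosed per group to obtain 20 pairs is 20/(1 - loss):

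- 5% loss: 20/0.95 = 21.1
- 10% loss: 20/0.90 = 22.2
- 20% loss: 20/0.80 = 25.0

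All lie well inside 40. The binomial chance of at least 20 analysable is:

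| Assumed loss | 40 recruited | 30 recruited |
|---|---|---|
| 20% | above 99.9% | 97.4% |
| 30% | 99.8% | 73.0% |
| 40% | 92.6% | 29.1% |
| 50% | 56.3% | 4.9% |

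**Precision forgone, ASL.** The variance of the mean paired difference is proportional to 1/pairs. With 40 recruited and 2, 4 or 8 people lost:

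- All lost pairs kept: 1 - 38/40 = 5%; 1 - 36/40 = 10%; 1 - 32/40 = 20%. These equal the assumed loss rates.
- Half kept: 1 - 38/39 = 2.6%; 1 - 36/38 = 5.3%; 1 - 32/36 = 11.1%.

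**Precision forgone, task.** Let s be the share of within-person variance due to run noise at 8 runs (assumed 0.3 to 0.7), with m of 8 runs left in one scan. The pair's variance is multiplied by 1 + s((8/m + 1)/2 - 1).

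- m = 6: 1.05 to 1.117
- m = 4: 1.15 to 1.35

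A kept pair thus carries between 1/1.35 = 74% and 1/1.05 = 95% of a full pair's information. With k kept pairs of weight w added to n full pairs, the variance cut is kw/(n + kw): 3.8-4.8% for 38 + 2, 7.6-9.6% for 36 + 4, and 15.6-19.2% for 32 + 8.

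**Adding single scans.** With n pairs, a extra scans in each condition and within-person correlation rho, the variance cut is a(1 - rho)/(n + a(1 - rho)).

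- n = 36, a = 2: 1/37 = 2.7% at rho 0.5; 0.4/36.4 = 1.1% at rho 0.8
- n = 32, a = 4: 2/34 = 5.9% at rho 0.5; 0.8/32.8 = 2.4% at rho 0.8

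**Bias.** The documents give nothing from which its size or direction can be derived. An illustration assumed a true effect of -0.50 SD, rho 0.6, 10% loss, and a selection correlation of -0.4 or +0.4 with the LEV value.

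- Completers: -0.469 or -0.531
- All usable scans, LEV scan lost: -0.449 or -0.551
- All usable scans, placebo scan lost: -0.500

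Neither analysis set is better throughout.

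**The case for a change.** The strongest case for a change is textual. Section 10.0 says people will be withdrawn and does not offer the milder step of dropping a run or a scan. Section 5.2 is a payment rationale that the analysis section never adopts, and it does not cover a person flagged at Visit 3 who already has two scans. Over-recruitment does not bring back a usable ASL pair from someone already dosed, nor does it define what counts as analysable. Fixing these details in advance would cost little and would guard against choices made after seeing the data, which 11.2.c allows by permitting alternative methods.

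It stands that no limit, analysis set or one-scan rule is written down. It does not stand that usable data will be discarded. The closing words of the quoted ground refer to scientific utility, so movement can fairly be read as one reason the scans would be of no use, and a session with most runs intact need not qualify.

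The 40-per-group figure is a ceiling. The allowance weakens if recruitment stops near 30 and losses reach 30% or more, as the table shows. That is a question of how many to enrol, which can be watched as analysable pairs accumulate.

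Bringing flagged people back for Visit 3 is also not free. At the assumed rates it means 2 to 8 more people per group attending for a capsule, a scan and a blood draw, some of whom may move again. The documents offer no basis for any particular motion limit. Who continues is for the investigator.

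**Conclusion.** No change to the plan is needed. The gap is one of detail. A competent imaging analyst would set a quality limit while blinded, judge ASL and task separately, estimate the LEV effect from people with two usable scans of that measure, and report losses by condition. Nothing in the documents prevents this, and section 5.2 already points to the two-scan set.

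The harm needs a harsher reading of section 10.0 than its words require. Even then, what can be shown is lost precision: up to 5%, 10% or 20% of variance at assumed losses of 5%, 10% or 20%, and about half that if only half the pairs are usable. The target of 20 analysable per group is met with 99.8% probability at 30% loss and 92.6% at 40%, provided 40 are recruited. Blinding limits selection to indirect drug effects on movement or anxiety, whose size at a single 500 mg dose is unknown, and neither analysis set is shown to be less biased. The conclusion rests on assumed loss rates and on recruitment running well above 20 per group.

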11.0 STATISTICAL CONSIDERATIONS

11.1 Data Management: All study data will be stored in a REDCap study database. The exception is for the raw and processed MRI scans that will be stored in the Vanderbilt XNAT Image Database system.

11.2 Statistical Analyses:

11.2.a. Drug levels: We will collect serum drug levels at the time of imaging to create a dose-response curve. The response will be defined as the change of a specific measure (hippocampal activity) from baseline. We will utilize nonlinear regression methods to create curves. Many studies have established a dose-response curve for epilepsy efficacy and safety (Boon et al., 2002; Meencke and Buyle, 2006; Rhee et al., 2017), but no dose-response curve currently exists for other measures such as imaging markers.

11.2.b. Clinical Data: The data will be used to better characterize the patients enrolled in this study.

11.2.c. Imaging Data: All images will be converted to an analyzable format. Spatial preprocessing will be performed using SPM5 (Functional Imaging Laboratory, London, UK) and FSL software (Analysis Group, FMRIB, Oxford, UK) or other comparable software. This will allow for realignment and transformation into a standardized space. Pairwise subtractions will then be performed, yielding images of mean difference and standard deviation, which can be used to produce z-scores and statistical parametric maps (SPMs). Statistical parametric maps will be constructed using a mixed effects model (subjects are considered random effects, conditions are considered fixed effects). SPM or other comparable software will allow us to test for condition effects, group effects, and group-by-condition interactions. Duration of illness and treatment will be assessed as confounding variables using an analysis of covariance. The duration of illness will be added into the fixed effects statistical model for the within group analysis as a covariate. Alternative methods will be employed when the data suggest a

more appropriate method. The effects of duration of illness and treatment on structural imaging data will be assessed by correlation analysis.

11.3 Power: We calculated power for our primary aim of modulation of hippocampal activity based on a similar study that detected changes in hippocampal activation between healthy controls and a group of aMCI patients receiving two weeks of oral LEV (Bakker et al., 2012). Using the effect sizes demonstrated in this paper, at N = 40 (healthy control sample N = 20; psychosis patient sample N = 20) and alpha = 0.05, we will have 80.3% power to detect a change in hippocampal activity.

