1.0 BACKGROUND

The purpose of this study is to test whether administration of levetiracetam (LEV), a commonly used anti-epileptic that alters neurotransmitter release, can reduce hippocampal hyperactivity. Specifically, we will utilize two functional magnetic resonance imaging (MRI) techniques: 1) blood oxygen level dependence (BOLD) contrast will assess activity with a visual scene processing task that engages the anterior hippocampus and 2) arterial spin labeling (ASL) will assess baseline activity. Previous studies in people with psychotic disorders have shown that the hippocampus is hyperactive and more activity correlates with worsening of clinical symptoms. Therefore, the aim of this study is to use an intervention to further understand the underlying mechanisms of the hippocampus in psychosis.

Background and Significance

The lifetime prevalence of schizophrenia is about 0.7% (Saha et al., 2005), and the burden of illness is significant not only for patients but also society at large (Lehman et al., 2004). One contribution to this massive disease burden is the lack of optimal treatments, as only 20% of diagnosed individuals reach favorable treatment outcomes (Association, 2016). An important factor in the lack of treatment development for psychotic disorders is the unavailability of predictors that can be used to determine if therapeutic candidates elicit their targeted biological effects (Tregellas, 2014).

A growing body of literature demonstrates that the anterior hippocampus is hyperactive in patients with schizophrenia (Schobel et al., 2009; Talati et al., 2014) and clinical high risk patients that progress to developing schizophrenia (Modinos et al., 2018; Schobel et al., 2013). This hyperactivity is the result of an excitation-inhibition imbalance in the hippocampus (Heckers and Konradi, 2015; Uhlhaas, 2013). Excitatory, glutamatergic pyramidal cells comprise 90% of hippocampus neurons (Olbrich and Braak, 1985). The remaining neurons are inhibitory, GABAergic interneurons that modulate and synchronize overall activity to exert ultimate hippocampus activity (Freund, 2003; Klausberger and Somogyi, 2008). Different models have attributed the hippocampal excitation-inhibition imbalance to alterations in neurotransmitters glutamate or GABA (Benes, 1999; Stan et al., 2015) or interneuron abnormalities (Heckers and Konradi, 2015; Lodge et al., 2009).

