5.0 ENROLLMENT

5.1. Recruitment: Study participants will be recruited from the **Psychiatric Genotype/Phenotype Repository (PGPR, IRB #080606)**: The PGPR study includes a clinical interview during which diagnostic and clinical history data is collected. At the end of this interview, individuals will be asked by one of the key research personnel listed on this application if they are interested in participating in the study. The PI of this study is the same PI for the PGPR study. Subjects will be read a script describing the study. Subjects will be told that the study is separate from their participation in the PGPR study and choosing not to participate in the study will not affect their participation in the PGPR study. In addition, individuals that have previously completed the PGPR study may be contacted and asked if they would like to participate in the study. The consent form for the PGPR study states that subjects may be contacted and asked if they would like to take part in future studies, if they agree. Subjects will be read a script telling them about the study. The telephone screening form used for the Psychiatric Genotype/Phenotype study will be re-administered to make sure that they still meet the original criteria for participating in the Psychiatric Genotype/Phenotype Study (i.e. age, physical health, and MRI requirements).

We will make every effort to recruit equal numbers of men and women. We will not exclude subjects based on gender or minority status. We minimize coercion throughout the study by repeatedly informing subjects that

they may discontinue study procedures at any point, or opt-out of any specific part of the study they become uncomfortable with completing.

We plan to recruit up to 80 subjects (up to 40 healthy control subjects and up to 40 patients with psychotic disorders) for the study. We hope to acquire analyzable data from at least 20 control subjects and 20 patients.

Subjects who were recently recruited in other psychiatry studies also conducted by this PI (e.g. genotype/phenotype studies) may not be required to participate in components of this study that would duplicate efforts (e.g. SCID interview). We plan to include data from those studies in the analyses of data from this study. Participants will be compensated for all activities they complete.

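### Section 11.2.a measures response from a baseline scan that is not scheduled, and with one active dose the dose-response part of Hypothesis 1 has no randomised test

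*Combined protocol and SAP*

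**What the plan says.** Section 11.2.a plans a dose-response curve from serum levels taken at imaging, fitted by nonlinear regression. Its outcome is defined thus: "The response will be defined as the change of a specific measure (hippocampal activity) from baseline". No model form, covariates or reference scan are given.

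On scans, section 6.4 says: "There will be a total of two MRI scans in this study (Visits 2, and 3"), and that at both visits "the participant will be scanned two hours after receiving the study intervention (LEV or placebo"). Under section 6.0, Visit 1 can be virtual.

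On dose, section 6.5 randomises participants to an order in which "they will receive two 250mg LEV capsules or two placebo capsules", with the other treatment at Visit 3. Section 7.5.a confirms a single 500 mg dose.

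Hypothesis 1 in section 2.0 reads: "Oral LEV will decrease, in a dose-response relationship, hippocampal activity in healthy control subjects and psychotic patients (ASL study").

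Section 11.2.c plans pairwise subtractions of images and tests of condition, group and group-by-condition effects.

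**The concern.** There are two separate problems.

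**No reference for the response.** A change from baseline needs a baseline measurement, and neither scheduled scan is taken before a capsule is given. An analyst following 11.2.a literally would have to choose a reference: the placebo scan, the first scan whatever the treatment, or a scan from an earlier study.

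**No randomised dose gradient.** With placebo and one active dose, randomisation identifies a single contrast. Among LEV scans, serum level differs only through characteristics that were not randomised. A fitted curve could still be reported as support for the dose-response part of Hypothesis 1, and the more so because 11.2.a notes that no such curve yet exists for imaging markers. If placebo scans are included at level zero, such a curve can be significant when the effect does not depend on level at all.

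**Working it through.** **1. Is there a baseline scan?** Section 6.4 gives two scans, both two hours post-capsule, so none of the two is pre-dose. The word baseline has other meanings elsewhere. In section 1.0 it is resting activity ("arterial spin labeling (ASL) will assess baseline activity"). In section 2.0 it refers to clinical ratings ("Following baseline clinical assessments, participants will undergo a 2-way crossover, double-blind, randomized controlled study with low-dose LEV and placebo"). Section 5.1 allows earlier data in ("We plan to include data from those studies in the analyses of data from this study"), but names no earlier scan as the reference. A participant given placebo first has a scan before any LEV; one given LEV first does not.

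**2. What varies the serum level?** Inputs: volume 0.5-0.7 L/kg (7.2; midpoint 0.6 used) and clearance 0.96 mL/min/kg = 0.0576 L/h/kg (7.3). Assuming immediate, complete absorption, C(2 h) = 500/(0.6 x W) x exp(-2 x 0.0576/0.6).
- At an assumed 70 kg: 9.8 mcg/mL. Section 6.5.b states 9.75, so the approximation agrees with the plan's own figure.
- At an assumed height of 1.70 m, the BMI limits of 17.5 and 45 give 50.6 kg and 130 kg, hence 13.6 and 5.3 mcg/mL.

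These are eligibility extremes, not an expected distribution. They show that body weight, which is not randomised, is a main source of variation in level.

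**3. Effect sizes.** Section 11.3 gives 80.3% power at 20 + 20 and alpha 0.05 without an effect size or test, so it cannot be reproduced forward. Solving power = 1 - F(t_0.975; df, delta) = 0.803 with the noncentral t, two-sided:
- paired, n = 40, delta = dz x sqrt(40): dz = 0.456
- paired, n = 20, delta = dz x sqrt(20): dz = 0.663
- two-sample, 20 v 20, delta = d x sqrt(10): d = 0.913

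The two-sample value is not an upper bound for a paired effect. Since dz = d/sqrt(2(1 - r)), a within-person correlation r above 0.5 gives dz above 0.91; at an assumed r = 0.7, dz = 0.913/sqrt(0.6) = 1.18.

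**4. Curve through placebo zeros when level does not matter.** Simulated difference D = LEV - placebo = -dz + 0.3 x sequence + N(0,1), with sequence coded +/-1. Levels are lognormal with an assumed CV of 15-40%; the documents give no CV. Share of datasets significant at 0.05:

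| Analysis | n = 40, dz 0.46 | n = 20, dz 0.66 |
|---|---|---|
| Straight line through zero | about 73-80% | about 73-79% |
| Emax curve through zero | 64-66% | 60-62% |
| Plain LEV-placebo test | about 80% | about 80% |

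**5. Slope among LEV scans only, effect truly proportional to level.** D = -dz x L + 0.3 x sequence + N(0,1), with L scaled to mean 1. D is regressed on L with sequence, and with group at n = 40 and 80. The approximate noncentrality is dz x CV x sqrt(n); for example 0.456 x 0.25 x 6.32 = 0.72, for which simulation gives about 11% power.

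| n | dz | Power, CV 15-40% |
|---|---|---|
| 20 | 0.66 | about 7-18% |
| 40 | 0.46 | about 7-19% |
| 40 | 0.91 | about 12-56% |
| 80 | 0.46 | about 8-36% |
| 80 | 0.66 | about 13-63% |
| 80 | 0.91 | about 21-87% |

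The 80 is the recruitment ceiling in section 5.1; 20 + 20 is the hoped-for minimum of analysable data.

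**The case against.** The strongest reply is that this is a labelling problem. With two scans per person, placebo is the only reference within the study, and the pairwise subtractions in 11.2.c point to it. That placebo comes second for some participants is ordinary crossover design. Section 11.2.a also says openly that its dose axis is measured serum level. All of this stands, and it is why the remedy is wording. It does not supply the missing definition or turn serum level into a randomised dose.

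Four stronger readings are tempting, and the documents do not support them.
- **Hypothesis 1 cannot be tested.** The LEV-versus-placebo part is tested by the condition effect in 11.2.c, and an exposure-response association can be estimated. Only a randomised test of the dose gradient is missing.
- **The slope has little power throughout.** Step 5 shows power above 80% in the most favourable cell, and larger effects are possible.
- **The slope is confounded by body weight.** The response is a within-person difference, so any stable effect of weight on hippocampal activity cancels. Weight confounds only if it alters drug response other than through serum level. The documents do not say that it does, so it may confound.
- **The imaging measure is undefined.** Section 11.2.a does not name it, but Hypothesis 1 ties the claim to ASL.

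Finally, 11.2.a plans neither a significance test nor placebo zeros. Step 4 shows what could happen if they were used, not what the plan commits to.

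**Conclusion.** The point holds and should be fixed. That no scheduled scan is pre-dose, and that only one active dose is given, follows directly from the text and needs no assumption.

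The sizes are illustrations. They rest on an assumed level CV of 15-40%, on effects back-solved from 80.3% power under a two-sided test, and on simple on/off or proportional effects. On that footing, a line through placebo zeros is significant almost as often as the plain LEV-placebo test even when level is irrelevant, so it adds no evidence of dose-response. The LEV-only slope is the more informative analysis, but its power is uncertain and often low, and the 80.3% in section 11.3 does not apply to it.

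**What to change.** **Section 2.0.** Restate Hypothesis 1 as a decrease in ASL hippocampal activity on LEV versus placebo in both groups, with any serum exposure-response relationship labelled exploratory.

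**Section 11.2.a.**
- Define response as the ASL hippocampal value at the LEV scan minus that at the placebo scan, whatever the visit order, with sequence/period and group in the model.
- Relabel the serum-level analysis as exploratory, observational exposure-response using the level in the LEV condition. Report the slope with a 95% confidence interval, and a body-weight-adjusted slope as a sensitivity analysis.
- State that no curve including placebo zeros will be cited as evidence of a dose-response relationship. Nonlinear curves may stay as description.

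**Cost.** Text changes in two sections. No new scans or blood samples are needed, and weight is already needed for the BMI criterion. The sponsor gives up a dose-response claim, and the slope's interval may be wide, more so after adjustment for weight.

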6.0 STUDY PROCEDURES

Overview: There are eight components of the study:

1. Screening and Consent
2. Diagnostic Interview (SCID)
3. Clinical Assessment (psychosis patients only)
4. MRI Scanning
5. Drug Administration
6. Venipuncture
7. Urine pregnancy test (for female participants)
8. Standardized Field-Sobriety Test

[figure not shown]

Figure 1: Study Design

Each component will be described in detail below. The entire study will be completed in three visits over the course of about one week, as demonstrated in **Figure 1**. Visit 1 can be completed virtually. Participants may be contacted by text message the day before the study to remind them of the study visit. The specific rating scales completed will be dependent upon diagnosis and the time since an individual participated in the PGPR study, as many of the measures overlap and assess symptomatology based on specific time-intervals (i.e., the last 2 weeks).

6.1 Screening and Consent: Subjects will be asked if they would like to participate in the current study. This screening will occur over the phone, electronically via zoom, or in person using the Screening Form. Informed consent will be obtained by study personnel directly involved in the research (i.e. research staff or graduate student). Personnel have completed IRB training and have considerable experience running studies on psychiatric populations. Informed consent will be obtained electronically via zoom or in the research offices at the Psychiatric Neuroimaging Program. A research staff member will explain the applicable procedures and the possible risks and benefits to the subjects. The details of the informed consent procedure are as follows:

1. The investigator or research staff and the subject will read together the entire consent form.
2. The subject will be asked details about the study. To document that the subject has read the consent form and has the capacity to understand the most important details, the investigator will use the appropriate Informed Consent Survey. The questions will be read by the investigator or research staff and the answers will be recorded (appropriate response listed in *Italics* in the Informed Consent

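### The imaging model for this two-period crossover names no visit (period) effect, and no balancing of treatment order is stated; a sizeable change between visits would cost power.

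*Combined protocol and SAP*

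**What the plan says.** Section 2.0 sets the design: "participants will undergo a 2-way crossover, double-blind, randomized controlled study with low-dose LEV and placebo". Section 6.4 fixes the imaging occasions: "There will be a total of two MRI scans in this study (Visits 2, and 3"). Section 6.5 describes allocation: "During Visit 2, participants will be randomly assigned to an intervention arm", with the other treatment given at Visit 3. The readable text gives no ratio, block size or stratification by diagnostic group. Section 6.0 refers to "Figure 1: Study Design", which was not visible in the copy reviewed.

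Section 11.2.c specifies a "mixed effects model (subjects are considered random effects, conditions are considered fixed effects") and says the software will allow the team to "test for condition effects, group effects, and group-by-condition interactions". It assesses duration of illness and treatment as confounders by analysis of covariance, and adds: "The duration of illness will be added into the fixed effects statistical model for the within group analysis as a covariate". The word conditions is not defined. A further sentence permits other methods if the data call for them, without naming any. Section 11.3 claims 80.3% power at "N = 40 (healthy control sample N = 20; psychosis patient sample N = 20") and alpha 0.05.

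**The concern.** In a two-period crossover every LEV-placebo difference is also a difference between two visits. If the imaging measure changes from Visit 2 to Visit 3 whatever the treatment, that change enters with a plus sign in participants given placebo first and a minus sign in those given LEV first.

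A model without a visit term leaves this change in the residual, so the standard error is too large. If the two orders turn out unequal in number, the change also shifts the LEV estimate in that trial. The shift is as likely to favour LEV as to oppose it.

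A visit change is plausible here, because the same participants repeat the same scanner task within about a week. Power is planned near 80% on 20 analysable participants per group, so there is little to spare. Visits are recorded, so a period term could be fitted afterwards. But choosing between the two models once the data are seen is what pre-specification should prevent.

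**Working it through.** **Inputs from the documents.** Two periods (2.0, 6.4, 6.5); 20 controls and 20 patients, alpha 0.05, power 80.3% (11.3).

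**Assumptions, because the documents are silent.** Two-sided tests; the same visit change in both groups; no carryover; visit change π = 0.25, 0.5 or 1.0 SD of the paired difference. The largest value exceeds every paired drug effect assumed below and serves only as an upper bound.

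**The stated power.** The 80.3% cannot be reproduced, because section 11.3 gives no effect size, SD or test. Solving the noncentral t power formula backwards gives the standardised effect that yields 80.3%:
- paired test, one group, n = 20: dz = 0.66
- paired test, both groups pooled, n = 40: dz = 0.46
- group-by-condition, 20 v 20: d = 0.91

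**Model.** For participant i, the LEV minus placebo difference is d_i = τ + s_i·π + e_i, with SD(e) = 1, s = +1 for placebo first and −1 for LEV first. The unadjusted test is the paired t test on d_i (n − 1 df). The adjusted test regresses d_i on s_i (n − 2 df), and its power does not depend on π. With balanced orders, omitting π inflates the SD of d_i from 1 to about √(1 + π²); at π = 0.5 this is √1.25 = 1.12.

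**Power averaged over the allocation:**

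| Test | Allocation | No term, π = 0 | π = 0.25 | π = 0.5 | π = 1.0 | With term, any π |
|---|---|---|---|---|---|---|
| Paired, n = 20 | 10:10 | 80.3% | 78% | 73% | 50% | 80.1% |
| Paired, n = 20 | simple random | 80.3% | 78% | 71% | 50% | 78% |
| Paired, n = 40 | 20:20 | 80.3% | 78% | 73% | 51% | 80.2% |
| Paired, n = 40 | simple random | 80.3% | 78% | 71% | 51% | 79% |
| Group-by-condition, 20 v 20 | balanced | 80% | 78% | 73% | 50% | 80% |
| Group-by-condition, 20 v 20 | simple random | 80% | 78% | 71% | 51% | 79% |

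The paired rows come from numerical integration and noncentral t; the group-by-condition rows come from 100,000 simulated trials per cell.

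**Break-even.** The term gains power only when π exceeds 0.09 SD (n = 20 at 10:10), 0.25 SD (n = 20, simple randomisation) or 0.17 SD (n = 40, simple randomisation).

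**Type I error without the term, n = 20.** Averaged over simple randomisation it is 5.0% to 5.1%. At 10:10 the test is conservative: 2.9% at π = 0.5.

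**One unequal split.** The shift in the unadjusted estimate is π × (n placebo-first − n LEV-first)/N. At 13:7 of 20 this is π × 6/20 = 0.30π, that is 0.075, 0.15 or 0.30 SD. Power is then 87%, 90% or 90% if the shift favours LEV and 68%, 50% or 12% if it opposes, against 76% with the term. Under simple 1:1 randomisation a split of 13:7 or worse has probability 26% (13% in the opposing direction). The same proportion in 40 participants, 26:14 or worse, has probability 8%.

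**The case against.** The strongest reply is that the loss rests on an assumed quantity. A visit change of 0.5 SD is 0.5/0.66 = 75% of the assumed drug effect at n = 20, and exceeds it in the pooled case (0.46). At half the drug effect (0.33 SD, n = 20) power is 77% against 80% when balanced, and 76% against 78% under simple randomisation. This stands, and the loss must be read as conditional.

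Second, 71% against 80% mixes two changes. Like for like at n = 20, the term alone is worth 80.1 − 72.7 = 7.4 points at 10:10 and 77.8 − 71.0 = 6.8 points under simple randomisation. This also stands.

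Third, section 5.1 plans up to 40 recruits per group. With dz 0.66, balanced orders and a 0.5 SD visit change, one-group power is about 90% without the term and 94% with it at n = 30, and 97% and 98% at n = 40. That is fair, but the stated power is at 20 per group, and 20 is the minimum the protocol hopes to analyse.

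Fourth, under unblocked randomisation the term lowers power when the visit change is small. This is correct, and is why the term and blocking belong together.

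Fifth, section 11.2.c may not be exhaustive: conditions is undefined and other methods are allowed. Neither commits the analysis to a period term. A balanced design in Figure 1 would settle allocation but would not supply the term.

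Last, the calculations are for a single summary measure, whereas the plan describes statistical maps, and the test behind the 80.3% is not identified. The figures show direction and rough size, not this trial's exact loss.

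**Conclusion.** The concern holds, as an improvement to consider. The plan names no period effect for a two-period crossover, and its readable text does not balance the orders. If the visit change is about 0.5 SD of the paired difference, the stated model gives up about 7 points of power for want of the term, and up to 9 compared with the term plus balanced orders. At 0.25 SD the loss is 0 to 2 points, and below that the term gains little or nothing.

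Over repeated randomisation the LEV estimate is unbiased and type I error is about 5%, so validity is not in question. An uneven split could still shift the estimate in the one trial that is run. All sizes depend on an assumed visit change and a drug effect back-solved from 80.3%. The 80.3% itself is not shown to be wrong.

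**What to change.** In section 11.2.c, define the treatment conditions as LEV and placebo, name visit (period) as a fixed effect beside condition, group and group-by-condition, and take the LEV minus placebo estimate from that model. In section 6.5, state 1:1 allocation to the two orders in small blocks within each diagnostic group. If Figure 1 already gives such a list, repeat it in the text. Adopt both changes together.

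The cost is one degree of freedom and a blocked list, with no new data or procedures. If there is no visit change, power falls from 80.3% to 80.1% at 10:10. The term without blocking would lower it to about 78% at n = 20 under simple randomisation, and to about 79% for the pooled and group-by-condition tests. Attrition can undo some of the balance: if 40 per group are allocated 20:20 and 20 remain at random, a split of 13:7 or worse has probability 11% and mean power with the term is 79%.
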